#### **5.2.4 Trial Blinding/Masking**

This is an open-label trial; therefore, the Sponsor, investigator and subject will know the treatment administered.

#### **5.3 Randomization or Treatment Allocation**

Subjects participating in this trial will be allocated to trial treatment by non-random assignment.

#### **5.4 Stratification**

No stratification based on age, sex or other characteristics will be used in this trial.

#### **5.5 Concomitant Medications/Vaccinations (allowed & prohibited)**

Medications or vaccinations specifically prohibited in the exclusion criteria are not allowed during the ongoing trial. Listed below are some specific restrictions for concomitant therapy or vaccination during the course of the trial. If there is a clinical indication for one of these or other medications or vaccinations specifically prohibited during the trial, discontinuation from trial therapy or vaccination may be required. The investigator should discuss any questions regarding this with the local Clinical Monitor. The final decision on any supportive therapy or vaccination rests with the investigator and/or the subject's primary physician. However, the decision to continue the subject on trial therapy or vaccination schedule requires the mutual agreement of the investigator, the Sponsor and the subject.

##### **5.5.1 Acceptable Concomitant Medications**

All treatments that the investigator considers necessary for a subject's welfare may be administered at the discretion of the investigator in keeping with the community standards of medical care. All concomitant medication will be recorded on the case report form including all prescription, over-the-counter (OTC), herbal supplements, and IV medications and fluids. If changes occur during the trial period, documentation of drug dosage, frequency, route, and date may also be included on the case report form. Subject may remain on anti-coagulation therapy as long as the prothrombin time or partial thromboplastin time is within therapeutic range of the intended use of anticoagulants.

All concomitant medications received within 28 days before the first dose of trial treatment and 30 days after the last dose of trial treatment should be recorded. Concomitant medications administered after 30 days after the last dose of trial treatment should be recorded for SAEs and ECIs as defined in Section 7.2.

For subjects enrolled in Cohort 5 (DLBCL), digoxin should be administered with caution. Please refer to the current version of the local prescribing information for lenalidomide for additional information.

## 5.5.2 Prohibited Concomitant Medications

Subjects are prohibited from receiving the following therapies during the Screening and Treatment Phase (including retreatment for post-complete response relapse) of this trial:

- Antineoplastic systemic chemotherapy or biological therapy
- GM-CSF
- Immunotherapy not specified in this protocol (IV Ig therapy is permissible)
- Chemotherapy not specified in this protocol
- Investigational agents other than pembrolizumab or lenalidomide
- Radiation therapy
  - Note: Radiation therapy to a symptomatic solitary lesion, plasmacytoma, bone lesions, or to the brain may be allowed after consultation with Sponsor.
- Live vaccines within 30 days prior to the first dose of trial treatment and while participating in the trial. Examples of live vaccines include, but are not limited to, the following: measles, mumps, rubella, chicken pox, yellow fever, rabies, Bacille Calmette-Guerin, and oral typhoid vaccine. Seasonal influenza vaccines for injection are generally killed virus vaccines and are allowed; however intranasal influenza vaccines (e.g., Flu-Mist®) are live attenuated vaccines, and are not allowed.
- Glucocorticoids for any purpose other than to modulate symptoms from an event of clinical interest of suspected immunologic etiology. The use of physiologic doses of corticosteroids may be approved after consultation with the Sponsor.
  - Note: Steroid premedications for contrast CTs are permissible.

Subjects who, in the assessment by the investigator, require the use of any of the aforementioned treatments for clinical management should be removed from the trial. Subjects may receive other medications that the investigator deems to be medically necessary.

The Exclusion Criteria describes other medications which are prohibited in this trial.

There are no prohibited therapies during the Post-Treatment Follow-up Phase.

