## 4.2.3 Rationale for Endpoints

### 4.2.3.1 Safety Endpoints

The primary safety objective of this study is to characterize the safety and tolerability of pembrolizumab or lenalidomide + pembrolizumab in subjects with hematologic malignancies. The primary safety analysis will be based on subjects who experienced toxicities as defined by CTCAE criteria. Safety will be assessed by quantifying the toxicities and grades experienced by subjects who have received pembrolizumab, or lenalidomide + pembrolizumab, including SAEs and events of clinical interest (ECIs).

Safety will be assessed by reported adverse experiences using CTCAE, Version 4.0. The attribution to drug, time-of-onset, duration of the event, its resolution, and any concomitant medications administered will be recorded. AEs will be analyzed including but not limited to all AEs, SAEs, fatal AEs, and laboratory changes.

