### **5.2.1.2 Dose Modification for Pembrolizumab**

AEs associated with pembrolizumab exposure may represent an immunologic etiology. These irAEs may occur shortly after the first dose or several months after the last dose of pembrolizumab treatment and may affect more than one body system simultaneously. Therefore, early recognition and initiation of treatment is critical to reduce complications. Based on existing clinical trial data, most irAEs were reversible and could be managed with interruptions of pembrolizumab, administration of corticosteroids and/or other supportive care. For suspected irAEs, ensure adequate evaluation to confirm etiology or exclude other causes. Additional procedures or tests such as bronchoscopy, endoscopy, skin biopsy may be included as part of the evaluation. Based on the severity of irAEs, withhold or permanently discontinue pembrolizumab and administer corticosteroids. Dose modification and toxicity management guidelines for irAEs associated with pembrolizumab are provided in [Table 5](#).

Table 5 Dose Modification and Toxicity Management Guidelines for Immune-related AEs Associated with Pembrolizumab

General instructions:				
Immune-related AEs	Toxicity grade or conditions (CTCAEv4.0)	Action taken to pembrolizumab	irAE management with corticosteroid and/or other therapies	Monitor and follow-up
Pneumonitis	Grade 2	Withhold	
 
Administer corticosteroids (initial dose of 1-2mg/kg prednisone or equivalent) followed by taper
 
	
 
Monitor participants for signs and symptoms of pneumonitis
 
Evaluate participants with suspected pneumonitis with radiographic imaging and initiate corticosteroid treatment
 
Add prophylactic antibiotics for opportunistic infections
 

	Grade 3 or 4, or recurrent grade 2	Permanently discontinue		

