Diarrhea / colitis	Grade 2 or 3	Withhold	
 
Administer corticosteroids (initial dose of 1-2mg/kg prednisone or equivalent) followed by taper
 
	
 
Monitor participants for signs and symptoms of enterocolitis (i.e., diarrhea, abdominal pain, blood or mucus in stool with or without fever) and of bowel perforation (i.e., peritoneal signs and ileus).
 
Participants with <math>\geq</math> Grade 2 diarrhea suspecting colitis should consider GI consultation and performing endoscopy to rule out colitis.
 
Participants with diarrhea/colitis should be advised to drink liberal quantities of clear fluids. If sufficient oral fluid intake is not feasible, fluid and electrolytes should be substituted via IV infusion.
 

	Grade 4	Permanently discontinue		

Immune-related AEs	Toxicity grade or conditions (CTCAEv4.0)	Action taken to pembrolizumab	irAE management with corticosteroid and/or other therapies	Monitor and follow-up
AST / ALT elevation or Increased Bilirubin	Grade 2	Withhold	
 
Administer corticosteroids (initial dose of 0.5- 1mg/kg prednisone or equivalent) followed by taper
 
	
 
Monitor with liver function tests (consider weekly or more frequently until liver enzyme value returned to baseline or is stable)
 

	Grade 3 or 4	Permanently discontinue	
 
Administer corticosteroids (initial dose of 1-2mg/kg prednisone or equivalent) followed by taper
 
	
Type 1 diabetes mellitus (T1DM) or Hyperglycemia	Newly onset T1DM or Grade 3 or 4 hyperglycemia associated with evidence of $\beta$ -cell failure	Withhold	
 
Initiate insulin replacement therapy for participants with T1DM
 
Administer anti-hyperglycemic in participants with hyperglycemia
 
	
 
Monitor participants for hyperglycemia or other signs and symptoms of diabetes.
 

Hypophysitis	Grade 2	Withhold	
 
Administer corticosteroids and initiate hormonal replacements as clinically indicated.
 
	
 
Monitor for signs and symptoms of hypophysitis (including hypopituitarism and adrenal insufficiency)
 

	Grade 3 or 4	Withhold or permanently discontinue 		

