### **7.2.3.2 Events of Clinical Interest**

Selected non-serious and serious adverse events are also known as Events of Clinical Interest (ECI) and must be reported to the Sponsor.

For the time period beginning when the consent form is signed until treatment allocation/randomization, any ECI, or follow up to an ECI, that occurs to any subject must be reported within 24 hours to the Sponsor if it causes the subject to be excluded from the trial, or is the result of a protocol-specified intervention, including but not limited to washout or discontinuation of usual therapy, diet, placebo treatment or a procedure.

For the time period beginning at treatment allocation/randomization through 90 days following cessation of treatment, or 30 days following cessation of treatment if the subject initiates new anticancer therapy, whichever is earlier, any ECI, or follow up to an ECI, whether or not related to the Sponsor's product, must be reported within 24 hours to the Sponsor, either by electronic media or paper. Electronic reporting procedures can be found in the EDC data entry guidelines. Paper reporting procedures can be found in the Investigator Trial File Binder (or equivalent).

Events of clinical interest for this trial include:

1. an overdose of Sponsor's product, as defined in Section 7.2.1 - Definition of an Overdose for This Protocol and Reporting of Overdose to the Sponsor, that is not associated with clinical symptoms or abnormal laboratory results.
2. an elevated AST or ALT lab value that is greater than or equal to 3X the upper limit of normal and an elevated total bilirubin lab value that is greater than or equal to 2X the upper limit of normal and, at the same time, an alkaline phosphatase lab value that is less than 2X the upper limit of normal, as determined by way of protocol-specified laboratory testing or unscheduled laboratory testing.\*

**\*Note:** These criteria are based upon available regulatory guidance documents. The purpose of the criteria is to specify a threshold of abnormal hepatic tests that may require an additional evaluation for an underlying etiology. The trial site guidance for assessment and follow up of these criteria can be found in the Investigator Trial File Binder.

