### 3. Follow-up Post-Allogeneic Stem Cell Transplantation

In the event a subject receives an allogeneic SCT within 24 months of the last dose of pembrolizumab, or before the end of the trial, the following events will be collected as ECIs through 18 months from the date of allogeneic SCT or until the end of the trial: GVHD, febrile syndrome treated with steroids, pulmonary complications, hepatic veno-occlusive disease and/or sinusoidal syndrome, immune-mediated AEs, critical illness, and transplant-related mortality. Post-allogeneic-SCT ECIs that occur after the normal safety follow-up period must be assessed for seriousness and causality and reported to the Sponsor as follows: within 24 hours if serious regardless of causality, or if non-serious and

considered to be drug-related; and 5 calendar days if non-serious and not considered to be drug-related. Guidance on details to be collected and suggested events to be reported can be found in the procedure manual.

If available and relevant to an event post allo-SCT, concomitant medications and/or laboratory results may be reported. Additional medically important AEs may be submitted at the Investigator's discretion.

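### Read literally, Section 5.5.2 bars the on-treatment corticosteroids that Table 5 directs for immune-related events, because its exception is tied to an ECI list with no general immune-related item (low severity)

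*Combined protocol and SAP*

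**What the plan says.** Section 5.5.2 lists therapies barred in the Screening and Treatment Phase, including retreatment. One entry is "Glucocorticoids for any purpose other than to modulate symptoms from an event of clinical interest of suspected immunologic etiology". Physiologic doses may be approved after Sponsor consultation, and steroid premedication for contrast CT is permitted. The section then says that subjects who, in the investigator's assessment, "require the use of any of the aforementioned treatments for clinical management should be removed from the trial". Nothing is prohibited in post-treatment follow-up.

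Section 4.2.3.1 uses the same lower-case phrase together with its abbreviation: "including SAEs and events of clinical interest (ECIs". Section 7.2.3.2 gives a numbered list, opened by "Events of clinical interest for this trial include":

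- Item 1 is an overdose without symptoms or abnormal laboratory results.
- Item 2 starts with "an elevated AST or ALT lab value that is greater than or equal to 3X the upper limit of normal" and also requires a bilirubin and an alkaline phosphatase threshold.
- Item 3 covers the period after allogeneic transplant, where "the following events will be collected as ECIs through 18 months from the date of allogeneic SCT". Immune-mediated events are named only in this item.

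Section 5.2.1.2 instructs: "Based on the severity of irAEs, withhold or permanently discontinue pembrolizumab and administer corticosteroids". For pneumonitis and for diarrhea/colitis, Table 5 says "Administer corticosteroids (initial dose of 1-2mg/kg prednisone or equivalent) followed by taper", and at the lower grades pembrolizumab is withheld, not stopped.

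**The concern.** The steroid exception in 5.5.2 depends on the event being an ECI, but most of the immune-related events for which Table 5 directs steroids are not on the ECI list. A site that follows Table 5 for a first Grade 2 pneumonitis gives a drug that 5.5.2, taken at its word, prohibits. The same site is then told to remove the subject, although Table 5 puts that subject on a hold. Section 5.8 also names only recurrent Grade 2 pneumonitis as a reason to stop.

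What is at stake is uniform conduct. One site may log a prohibited-medication deviation, another may log nothing, and a third may take the subject off study. Section 5.8 separates stopping treatment from leaving the trial, and 5.5.2 does not, so a literal removal could also end follow-up for that subject.

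**Working it through.** No plan figure is involved. The check sets the texts side by side and counts rows in Table 5.

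**Step 1: which use is affected.** Because 5.5.2 lifts all prohibitions in post-treatment follow-up, grades that require permanent discontinuation are left aside. Only corticosteroid use with pembrolizumab withheld is counted.

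**Step 2: Table 5 rows.**

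| Row | Withhold grade | Steroid wording | Within the 5.5.2 allowances as worded? |
|---|---|---|---|
| Pneumonitis | 2 | unconditional | no |
| Diarrhea/colitis | 2 or 3 | unconditional | no |
| AST/ALT or bilirubin | 2 | unconditional | only if ECI item 2 is fully met |
| Nephritis | 2 | unconditional | no |
| Hypophysitis | 2; 3 or 4 at discretion | if clinically indicated | partly, through physiologic doses |
| Myocarditis | 1 or 2 | depends on severity | no |
| All other immune-related | persistent or intolerable 2; some 3 | depends on type and severity | no |
| T1DM/hyperglycemia, hyperthyroidism, hypothyroidism | not relevant | none | not at issue |

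**Step 3: count.**

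- Rows in total: 10. Rows without corticosteroid wording: 3. Rows with corticosteroids and a withhold grade: 10 − 3 = 7.
- Of these, 4 are unconditional and 3 conditional (4 + 3 = 7).
- Rows that can meet an ECI item on treatment: at most 1, the hepatic row. That needs AST or ALT at least 3X ULN, total bilirubin at least 2X ULN and alkaline phosphatase below 2X ULN together.
- Rows outside the ECI exception: 7 − 1 = 6, of which 4 − 1 = 3 are unconditional and 3 are conditional.
- Setting aside hypophysitis, which may partly fit the physiologic-dose allowance, leaves 6 − 1 = 5 rows wholly outside.

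**Step 4: could another ECI item help?** Item 1 is not immunologic. Item 3 applies after an allogeneic transplant, and Section 7.1.5.3.3 moves subjects who stop treatment for transplant into survival follow-up, where 5.5.2 bars nothing.

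**Step 5: could another allowance in 5.5.2 help?** The prednisone doses of 1-2 mg/kg directed for pneumonitis, colitis and nephritis are treatment doses, not physiologic replacement. CT premedication is irrelevant.

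**Step 6: infusion reactions.** Table 9 lists corticosteroids among the options for Grade 3 or 4 infusion reactions. These are not ECIs either, so the same wording problem arises. There the subject stops trial treatment anyway, so no hold is disturbed.

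**The case against.** The strongest reply is that the literal reading is not forced. The phrase in 5.5.2 is lower case, without abbreviation or cross-reference, whereas 5.5.1 points expressly to ECIs as defined in Section 7.2. The list in 7.2.3.2 is introduced by a word that need not mean a closed list. On the literal reading the exception is nearly empty on treatment, while an ordinary-language reading gives it content and agrees with Table 5. This reading is possible but weak. Section 4.2.3.1 attaches the abbreviation to the same lower-case words, and a numbered list carrying 24-hour reporting is not one that sites would extend themselves.

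The second reply carries more weight. Section 5.5 says discontinuation may be required, leaves the final decision on supportive therapy to the investigator or primary physician, and makes continuation a matter of agreement between investigator, Sponsor and subject. Section 5.5.1 lets investigators give what they consider necessary. Section 5.6.1 repeats the oral or IV steroid guidance and expects several tapers. Together these make the intent plain and soften the consequence, but they do not correct 5.5.2, which is the specific rule and has no cross-reference to Table 5.

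Reach is also limited. Enrollment in Cohorts 1 and 3 is complete, Cohort 2 is off treatment, Cohort 5 has been discontinued, and the current amendment exists to let the study close.

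**Conclusion.** The point holds as a low-severity rule that is wrong as written. Taken literally, 5.5.2 prohibits corticosteroids that 5.2.1.2 and Table 5 direct while pembrolizumab is withheld, and calls for removal from the trial of subjects who need them. The size is 6 of 7 relevant rows outside the ECI exception, 5 of them with no partial cover elsewhere. These are rows, not subjects; the documents do not say how many subjects remain on treatment or retreatment.

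The conclusion assumes that the phrase in 5.5.2 carries its defined meaning. It also assumes that the general-instructions cell of Table 5, which has no content in the available text, does not settle the matter.

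A reader might infer more, in three ways, and the documents do not support any of them:

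- *That subjects would be denied steroids for immune toxicity.* Sections 5.2.1.2, 5.5, 5.5.1 and 5.6.1 all point the other way, and most sites would probably follow Table 5.
- *That the response results, power or type I error are compromised.* No figure in the plan depends on this rule, and nothing shows how often a removal would occur.
- *That the document history proves an error.* It records an intention to stop reporting immune-related events as ECIs, which may explain the mismatch, but it describes superseded text. The finding rests on the current sections alone.

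**What to change.** In Section 5.5.2, replace the reference to an event of clinical interest of suspected immune cause with: *an adverse event of suspected immunologic etiology (managed per Table 5) or an infusion reaction (managed per Table 9)*. The second part is needed because a reference to Table 5 alone would leave the corticosteroids in Table 9 barred.

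The sentence on removal should stay as it is. Rewriting it would change the consequence for every prohibited therapy, which goes beyond this error.

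The cost is one phrase. Data collection, ECI reporting, analysis and sample size do not change.

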Treatment with pembrolizumab or lenalidomide + pembrolizumab combination will continue until documented disease progression, unacceptable AEs, intercurrent illness that prevents further administration of treatment, investigator's decision to withdraw the subject, subject withdraws consent, pregnancy of the subject, noncompliance with trial treatment or procedure requirements, or administrative reasons requiring cessation of treatment. Per the investigator's discretion subjects who attain an investigator-determined confirmed complete response (CR) or stringent complete response (sCR) (MM) may consider stopping trial treatment after receiving at least 24 weeks of therapy. At least two doses of pembrolizumab must be received after CR or sCR (MM) is documented for subjects receiving pembrolizumab monotherapy. An additional 21 consecutive daily doses of lenalidomide + 2 doses of pembrolizumab must be received after CR is documented in subjects in Cohort 5 (DLBCL). These subjects will be eligible for retreatment after they have experienced disease progression at the discretion of the investigator if no cancer treatment was administered since the last dose of trial treatment, the subject still meets the safety parameters listed in the Inclusion/Exclusion criteria, and the trial remains open (refer to Section 7.1.5.2.1 for further details). After the end of treatment, each subject will be followed for the occurrence of AEs and spontaneously reported pregnancy as described under Section 7.2 of the protocol. Subjects who discontinue treatment for reasons other than disease progression will have post-treatment follow-up for at least 12 months for disease status until disease progression, initiating a non-study cancer treatment, withdrawing consent, or becoming lost to follow-up. All subjects will be followed by telephone contact for at least 12 months after their discontinuation visit for overall survival (OS) until death, withdrawal of consent or the end of the study, whichever comes first.

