#### **5.8 Subject Withdrawal/Discontinuation Criteria**

Subjects may withdraw consent at any time for any reason or be dropped from the trial at the discretion of the investigator should any untoward effect occur. In addition, a subject may be withdrawn by the investigator or the Sponsor if enrollment into the trial is inappropriate, the trial plan is violated, or for administrative and/or other safety reasons. Specific details regarding discontinuation or withdrawal procedures; including specific details regarding withdrawal from Future Biomedical Research, are provided in Section 7.1.4 – Other Procedures.

A subject must be discontinued from treatment (but may continue to be monitored in the trial) for any of the following reasons:

- The subject or legal representative (such as a parent or legal guardian) withdraws consent for treatment.
- Confirmed disease progression per respective response assessment criteria

Note: A subject may be granted an exception to continue on treatment with confirmed progression if clinically stable or clinically improved, please see Section 7.1.2.7.7.

- Unacceptable adverse experiences as described in Section 7.2.
- Any progression or recurrence of any malignancy, or any occurrence of another malignancy requires active treatment
- Intercurrent illness other than another malignancy as noted above that prevents further administration of treatment.
- Recurrent Grade 2 pneumonitis
- Investigator's decision to withdraw the subject
- The subject has a confirmed positive serum pregnancy test
- Noncompliance with trial treatment or procedure requirements

- The subject is lost to follow-up
- Administrative reasons

The End of Treatment and Follow-up visit procedures are listed in Section 6.0 (Protocol Flow Chart) and Section 7.1.5 (Visit Requirements). After the end of treatment, each subject will be followed for 30 days for AE monitoring (SAEs will be collected for 90 days after the end of treatment as described in Section 7.2.3.1). Subjects who discontinue for reasons other than PD will have post-treatment follow-up for disease status until disease progression, initiating a non-study cancer treatment, withdrawing consent or becoming lost to follow-up. After documented disease progression or the start of new antineoplastic therapy each subject will be followed by telephone for OS until death, withdrawal of consent, or the end of the study, whichever occurs first.

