#### **7.1.1.6.3 Subsequent Antineoplastic Therapy Status**

The investigator or qualified designee will review all new antineoplastic therapy initiated after the last dose of trial treatment, and collect transplant parameters (e.g., date and type of transplant, conditioning regimen) when applicable. If a subject initiates a new antineoplastic therapy within 30 days after the last dose of trial treatment, the 30-day Safety Follow-up visit must occur before the first dose of the new therapy. Once new antineoplastic therapy has been initiated the subject will move into survival follow-up.

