#### **8.2.4 Analysis Populations**

##### **8.2.4.1 Efficacy Analysis Populations**

The FAS population will serve as the primary population for the analysis of efficacy data in this study. The FAS population consists of all randomized subjects in each disease cohort who:

- Receive at least one dose of study treatment,
- Have a baseline disease assessment, and
- Have a post baseline disease assessment OR discontinue the trial due to PD/drug related AE

Supportive analyses will be conducted in the ITT population, defined as all randomized subjects.

For MDS cohort only, two additional subpopulations FAS/WHO-Classification and ITT/WHO-Classification will be used. These two populations have the same definition as above except for requiring the baseline disease assessment to satisfy WHO criteria.

Subjects will be included in the treatment group to which they are randomized for the analysis of efficacy data. Details on the approach to handling missing data are provided in Section 8.2.5 Statistical Methods.

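### Section 5.5.2 tells sites to take subjects who need a prohibited therapy out of the trial, contradicting the protocol's own follow-up rules; read literally, it censors OS, probably informatively

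*Combined protocol and SAP*

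**What the plan says.** Section 5.5.2 lists therapies not allowed during screening and treatment: other systemic anticancer drugs and biologics, unspecified immunotherapy, other investigational agents, radiation, GM-CSF, live vaccines and most glucocorticoid use. It then says that subjects who, in the investigator's judgement, "require the use of any of the aforementioned treatments for clinical management should be removed from the trial". Its last line adds: "There are no prohibited therapies during the Post-Treatment Follow-up Phase".

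Other sections describe a different consequence:

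- Section 5.5, the parent section, says that where there is an indication for a medication "specifically prohibited during the trial, discontinuation from trial therapy or vaccination may be required".
- Section 5.8 opens its list of reasons for stopping with "A subject must be discontinued from treatment (but may continue to be monitored in the trial) for any of the following reasons", and continues: "Subjects who discontinue for reasons other than PD will have post-treatment follow-up for disease status until disease progression" (or new cancer treatment, withdrawn consent or loss to follow-up).
- Section 2.1: "All subjects will be followed by telephone contact for at least 12 months after their discontinuation visit for overall survival".
- Section 7.1.1.6.3: "Once new antineoplastic therapy has been initiated the subject will move into survival follow-up". Section 7.1.5.3.3 says the same and sets telephone contact about every 12 weeks.

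For the primary population, Section 8.2.4.1 requires a dose, a baseline assessment, and that subjects "Have a post baseline disease assessment OR discontinue the trial due to PD/drug related AE". The summary definition in Section 8.1.1 asks for a baseline and a post-baseline evaluation and has no such exception. Missing response within the FAS counts as non-response (Section 8.2.5.1), ITT is supportive, and time-to-event data are censored at the last assessment (Table 17).

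**The concern.** The same event, starting another anticancer drug while on trial treatment, triggers removal from the trial in 5.5.2 and entry into survival follow-up in 7.1.1.6.3. A site cannot do both. Section 5.8 separates stopping treatment from leaving the trial, so a site that reads 5.5.2 as meaning the trial is not being careless.

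OS is a secondary endpoint in every cohort. A subject removed at that moment is censored for OS. Needing another anticancer therapy plausibly marks a higher risk of death, so the Kaplan-Meier assumption that censored subjects resemble those remaining would fail, and survival would look better than it was.

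A related gap lies in the analysis set. A subject who leaves before any post-baseline assessment, with neither PD nor a drug-related AE as the recorded reason, is in no FAS definition and drops out of the primary denominator.

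**Working it through.** **1. Who is exposed.** Section 5.5.2 governs only the screening and treatment phase. A subject with confirmed PD normally stops treatment under 5.8 and enters survival follow-up under 7.1.5.3.3, where nothing is prohibited. The exposed group is therefore mainly on-treatment subjects without confirmed PD who need a listed therapy. The documents give no expected or observed number of these.

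**2. OS: direction.** Suppose a fraction f is removed early. Let true survival at time t be S_K in those kept and S_R in those removed. The truth is (1 − f)·S_K + f·S_R. Kaplan-Meier, with the removed censored, estimates about S_K. The error is S_K − [(1 − f)·S_K + f·S_R] = f·(S_K − S_R). It is positive when S_R < S_K and cannot exceed f. Neither f nor S_R is in the documents, so no figure in months or percentage points can be given.

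**3. PFS and TTP: item by item.** For chemotherapy, biologics, immunotherapy and investigational anticancer agents, Sections 5.8 and 7.1.5.3.2 end disease-status follow-up at new antineoplastic therapy anyway, so literal removal costs little disease assessment. The added loss is mainly for glucocorticoids, GM-CSF, live vaccines and arguably radiation, where 5.8 would have continued assessment. Later deaths would also be lost if they count as PFS events; the SAP gives no PFS definition or censoring rule for new therapy.

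**4. FAS: arithmetic.** Plan's figures first, by exact binomial tail P(X ≥ r | n, p), from Section 8.2.7 (one-sided 5%, about 80% power):

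| Cohort | Rule | Null, alternative | Type I error | Power |
|---|---|---|---|---|
| 1 and 3 | 6/25 | 10%, 30% | 0.033 | 0.807 |
| 2 | 12/28 | 25%, 50% | 0.029 | 0.828 |
| 4 | 27/78 | 25%, 39% | 0.037 | 0.818 |

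The rules hold, with Cohort 2 somewhat above its stated power.

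Now assume that a fraction f of enrolled subjects, all non-responders, falls outside the FAS, and that enrolment is topped up to the planned evaluable number, as 8.2.7 allows. If the true rate among all enrolled is the null rate p0, the rate within the FAS is p0/(1 − f). At f = 4% this is 0.10/0.96 = 0.1042 or 0.25/0.96 = 0.2604; at f = 20%, 0.125 or 0.3125. The chance of declaring success becomes:

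| f (assumed) | 6/25 | 12/28 | 27/78 |
|---|---|---|---|
| 0% | 0.033 | 0.029 | 0.037 |
| 4% | 0.040 | 0.040 | 0.058 |
| 8% | 0.048 | 0.054 | 0.091 |
| 12% | 0.057 | 0.072 | 0.138 |
| 20% | 0.083 | 0.132 | 0.298 |

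Here f covers every early stop for a reason other than PD or a drug-related AE, not only those arising from 5.5.2.

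**The case against.** The best reply is that the rest of the protocol settles the meaning. Five sections and the flow-chart footnotes keep subjects in survival follow-up after new therapy, the last line of 5.5.2 presupposes it, and Section 7.1.5.4 lets the sponsor request survival status for anyone without a scheduled contact. Harm requires a site to follow one sentence over all of these. That is fair and lowers the likelihood, but the sentence is a direct instruction to sites and remains wrong as written.

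Timing also counts. This amendment serves study closure, enrolment in Cohorts 1 and 3 was complete by Amendment 04, and Cohorts 2 and 5 are closed. That limits how many subjects can still be affected; it does not remove the contradiction or change how the FAS is built at analysis.

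Three stronger readings are tempting, and the documents do not support them.

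- A reader might infer that PFS and TTP are seriously biased. Step 3 shows that little disease assessment is lost. TTP is an endpoint only in Cohort 2, where all subjects have already stopped treatment.
- A reader might put a size on the OS bias by censoring a share of progressors at progression. Those subjects are mostly routed to survival follow-up already, so that models the wrong group, and no share is documented.
- A reader might infer that 5.5.2 strips the sickest subjects from the FAS. Section 8.2.4.1 retains those who discontinue for PD or a drug-related AE. First assessments come at Weeks 3 to 6 in Cohorts 1 and 2 and in the Q3W lymphoma cohorts. Lymphoma imaging may be brought forward for clinical progression, and an assessment is called for at discontinuation without confirmed PD. Nor do all listed items mark poor prognosis: live vaccines and GM-CSF are on the list. The gap belongs to the FAS definitions and would remain if the 5.5.2 sentence were deleted.

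**Conclusion.** The contradiction is real and should be corrected. If 5.5.2 is read literally, OS is censored when an on-treatment subject needs another anticancer therapy, probably informatively and upward. This rests on two assumptions: that some sites read it that way, and that such subjects have worse survival than those who remain. The error in survival probability is at most the fraction removed, which is unknown. OS is summarised descriptively with no hypothesis test, so no formal conclusion depends on it. The added effect on PFS is limited mainly to non-antineoplastic items.

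The FAS issue is separate and narrow, but it touches the primary endpoint. Under the assumptions in step 4, one or two such losses in 25 keep Cohorts 1 and 3 below 5%, whereas Cohort 4 is above 5% at a 4% loss. The true rate of loss is not documented, and the supportive ITT analysis would show a discrepancy without changing the primary result.

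**What to change.** Protocol: reconcile 5.5.2 with 2.1, 5.5, 5.8, 7.1.1.6.3 and 7.1.5.3. Replace the instruction to remove subjects from the trial with a statement that they remain in the disease-status and survival follow-up the protocol already schedules. Whether trial treatment stops, and which therapies are prohibited, stay with the sponsor's existing rules. The cost is one sentence and no new visits.

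SAP: make the FAS definitions in 8.1.1 and 8.2.4.1 identical, and count every treated subject with a baseline assessment but no post-baseline assessment as a non-responder, whatever the reason for discontinuation. This is a separate edit. Its downside is a slightly lower reported response rate.
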